2.9 Safety Analyses

Safety endpoints will be summarized with descriptive statistics. All safety summaries and analyses will be performed using the safety population. Vital signs, laboratory, and ECG results will be summarized by timepoint and treatment. Adverse events and concomitant medications/procedures will be summarized overall.

Prior and concomitant medications and procedures will be coded by the World Health Organization (WHO) Drug Dictionary version 2018/Q3. Medications and procedures will be considered concomitant unless they ended prior to treatment.

3 SUMMARY TABLES, LISTINGS, AND FIGURES

3.1 General Conventions

Unless otherwise stated, summary statistics including the number of subjects (n), mean, standard deviation, median, minimum and maximum will be presented for continuous variables. Generally, the minimum and maximum values will be presented to the same decimal precision as the raw values, the mean and median values to one more, and the standard deviation, to two more decimal places than the raw values. For categorical variables, per category, the absolute counts (n) and percentages (%) of subjects with data. Percentages will be presented to one decimal place.

For AEs, medical history and concomitant medications will be reported on a per-subject basis. The denominator for the percentage calculation will be the number of subjects at risk in each treatment group. A subject will be considered at risk if the subject is in the analysis set and in the subgroup of interest.

All p-values will be rounded to 4 decimal places. If a p-value is less than 0.0001 it will be displayed as “< 0.0001”, a p-value rounding to 1 will be displayed as “> 0.9999”.

Unless otherwise specified, all summaries will be performed by treatment group, all efficacy analyses will be based upon the FAP population, and all safety analyses will be based upon the safety population.

3.2 Definition of Baseline

Unless specified elsewhere, baseline is defined as the last available measurement prior to administration of study drug. For events that occur on the same day as the first administration of study drug (i.e. assessments performed at the Baseline visit), the assessment will be classified as pre-treatment, hence baseline. Baseline for the daily measures that are recorded in the eDiary are defined in [Table 4](#).

3.3 Clinical Study Subjects

3.3.1 Subject Disposition and Analysis Populations.

The number of subjects randomized, treated, and discontinued early, will be summarized within all randomized subjects. The reason for early termination will be summarized. Additionally, a summary of subjects who attended each visit as determined by the presence of a vital signs result.

A listing of entry criteria that were not met will be produced. The listed criteria will include the criteria language. A table of the violated entry criteria for randomized subjects will be produced, as well as a table that summarizes the screen failure reasons for screen failure subjects.

The number of subjects in each analysis population will be summarized.

3.3.2 *Demographics and Baseline Characteristics*

Demographic and baseline characteristics will be summarized descriptively by treatment group. This will include the following items:

- Age – continuous and categories (≤ 64 years, > 64 years) and (< 50 years, ≥ 50 years).
- Race
- Ethnicity
- Sex
- Height
- Weight
- Baseline WI-NRS – continuous and categories (< 8.5 , ≥ 8.5)
- Screening WI-NRS
- Baseline WI-VAS
- Length of chronic pruritus – continuous and categories (<1 yr, 1-5 yrs, >5 yrs)
- Location of pruritus
- Randomization strata
- Protocol version screened under

The reproductive measures (e.g. child bearing potential, surgical sterilization procedure, method of contraception, female subject specific medical history) will be listed but otherwise not tabulated.

The serology, serum IgE, iron, other labs and additional tests sites perform to confirm entry criteria results will be listed but otherwise not tabulated.

3.3.3 *Concomitant Medications and Procedures*

Medications and procedures with a stop date before the treatment dosing date will be considered prior medications/procedures. Medications/procedures with a start or stop date on or after the treatment dosing date will be considered concomitant. All medications/procedures marked as ongoing are concomitant.

A medication/procedure with an incomplete stop date will be considered concomitant if:

1. Month is missing and year is equal to or after the year of treatment dosing date
2. Day is missing and year is equal to the year of the treatment dosing date and month is equal to or after the month of the treatment dosing date.

All concomitant medications and procedures will be summarized by treatment group. All medications/procedures, including prior medications/procedures, will be provided in listings.

A table will be produced to summarize rescue medications used for intercurrent events defined in [Section 2.6](#).

3.3.4 Medical History

Medical history will be tabulated by system organ class, preferred terms and treatment group and provided in a listing. The female specific medical history will be listed separately from other medical history.

3.3.5 Clinical Study Treatment

The total tablets used, duration of treatment, and compliance (see [Section 2.2](#)) will be summarized. The days of dosing as measured by the eDiary will be summarized. All eDC study drug data will be listed, including lost tablets. The days of dosing from the eDiary will be listed, but the daily results will not.

3.4 Analysis of Efficacy Endpoints

3.4.1 Calculation Examples for Daily Measures

Below are examples of how the eDiary WI-NRS weekly results will be calculated based upon windows outlined in [Table 4](#) and rules outlined in [Section 2.4](#).

1. Example 1 (complete data)
 - a. The subject has results for all seven days leading up to the visit (e.g. $x_8, x_9, x_{10}, x_{11}, x_{12}, x_{13}, x_{14}$).
 - b. The average for Week 2 is $(x_8 + x_9 + x_{10} + x_{11} + x_{12} + x_{13} + x_{14})/7$.
2. Example 2 (incomplete data, completed in the extended range)
 - a. The subject has results for less than seven days in the original range (e.g. $x_{22}, x_{24}, x_{25}, x_{27}, x_{28}$) but have enough in the extended range to reach seven results overall (e.g. x_{29}, x_{31}). In this example the subject is missing diary data on days 23, 26, and 30.
 - b. The average for Week 4 is $(x_{22} + x_{24} + x_{25} + x_{27} + x_{28} + x_{29} + x_{31})/7$.
3. Example 3 (incomplete data)

- a. The subject has results for less than seven days in the original range (e.g. x_{39} , x_{40} , x_{42}) and does not have enough in the extended range to reach seven results overall (e.g. x_{44} , x_{46}). In this example the subject is missing diary data on days 36, 37, 38, 41, 43 and 45.
 - The average for Week 6 is $(x_{39}+x_{40}+x_{42}+x_{44}+x_{46})/5$.
4. Example 4 (no data)
 - a. The subject does not complete the diary from day 60 onwards.
 - b. The average for Week 10 is missing and the missing data rules ([Section 2.7](#)) are used.

3.4.2 *WI-NRS*

The WI-NRS endpoints (result, change from baseline, 3-point and 4-point responders) will be summarized at the primary time point (Week 10) as well as at Weeks 2, 4, 6, 8 and Follow-up. The summary measures will include 95% Wald confidence intervals for the treatment difference and a p-value for the treatment difference (for the change from baseline and responder rate measures). The baseline WI-NRS will also be summarized, but no confidence interval will be produced. A graph of the mean WI-NRS results and mean change from baseline results and the 4-point responder rate (baseline included with a rate of zero) by timepoint and treatment will be produced.

The WI-NRS scores for days 1 to 14 will be plotted by averaging the available data across subjects within treatment group and study day. These results will be summarized in a table along with change from baseline, where baseline is defined in the identical manner used for the weekly measures. Daily WI-NRS results will be summarized in a table based upon availability of the data regardless of any intercurrent events.

The test used for the 3 and 4-point responder rates at Weeks 2, 4, 6, 8 and 10 is a CMH test controlling for the ‘as randomized’ stratification factors. The ‘as randomized’ stratification factors are based upon the stratification cell that the subject was randomized to. The differences between treatment groups for the change from baseline measure will be tested using an ANOVA model controlling for the stratification factors. A main effects model with an interaction term (treatment by stratification factors) and a Type II hypothesis will be used. The estimated treatment effect from this test will be a weighted average based upon the equation provided in [Section 2.5](#).

The WI-NRS 4-point responder rates at Week 10 will be summarized within the subgroups and separately by the post baseline factors outlined in [Section 2.8](#). Forest plots based upon the same groups will also be produced.

A missing data sensitivity analysis will be conducted using the multiple imputation method outlined in [Section 2.8](#). This analysis will include summary statistics by time points for the 4-point WI-NRS responder rate and the continuous WI-NRS measures as well as testing for the 4-point WI-NRS responder endpoint at Week 10. The following steps will be followed:

1. Using the daily eDiary data, the windows in Table 4 and the intercurrent rules outlined in Section 2.6 calculate the weekly WI-NRS values. Within this will be unknown values (i.e. no data within the Table 4 windows)
2. The missing WI-NRS values will be filled in using the MCMC method to generate at least 1000 datasets. [REDACTED] CCI [REDACTED]
[REDACTED]
[REDACTED]
[REDACTED]
3. From each dataset the responder status will be determined.
4. The resulting point estimates (Mantel Haenszel treatment effect and standard error) and the responder rate p-value from the data will be calculated using the SAS software procedure Freq.
5. These results will be combined with the SAS software procedure mianalyze.

3.4.3 *WI-VAS*

The WI-VAS endpoint will be summarized with descriptive statistics at Baseline, Weeks 2, 4, 6, 10 and Follow-up. The summary measures will include 95% Wald confidence intervals of the treatment difference. In addition, a graph of the mean score by treatment and timepoint will be produced. The differences between treatment groups for the change from baseline measure will be tested using an ANOVA model similar to the WI-NRS endpoint.

3.4.4 *Exploratory Endpoints*

The ESS endpoint will be summarized at Baseline, Weeks 2, 4, 6, 10 and Follow-up. The total score and change from baseline in the total score will be summarized. The difference in average scores between treatment group will be summarized.

The sPGA endpoint will be summarized at Baseline, Weeks 2, 4, 6, 10 and Follow-up. The categorical result (e.g. Mild, Moderate, ...) will be summarized at each timepoint for each treatment group.

The PGIC will be summarized at Weeks 2, 4, 6, 10 and Follow-up. The categorical result will be summarized at each timepoint.

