6.1 Efficacy Parameters

6.1.1 *Itch Numeric Rating Scale*

The Itch NRS is a validated, self-reported instrument for measurement of itch intensity. It uses a 24-hour recall period and asks subjects to rate the intensity of their itch on an 11-point scale ranging from 0 (no itch) to 10 (worst itch imaginable). Higher scores indicate greater itch intensity. The questionnaire is provided in [Appendix C](#).

During the study, WI-NRS assessments will be reported by the subject via eDiary. Subjects will record their WI-NRS scores once daily at approximately the same time each day (+/- 3 hours) throughout the screening, treatment, and follow-up periods, as outlined in [Appendix A](#). Subjects may be allowed to adjust the timing of eDiary completion within the first week of Screening as needed. Standardized training and instructions will be provided to all subjects prior to eDiary use.

6.1.2 *Itch Visual Analog Scale*

The Itch VAS is a validated, self-reported instrument for measurement of itch intensity. It uses a 24-hour recall period and asks subjects to rate the intensity of their worst itch on a 100-mm horizontal line ranging from 0 mm (no itch) to 100 mm (worst itch imaginable). Higher scores indicate greater itch intensity. The VAS measurement will be summarized in centimeters. Standardized paper questionnaires will be distributed to sites and, in order to ensure consistency, cannot be copied, printed, or faxed.

During the study, WI-VAS assessments will be reported by the subject via a paper form administered at study visits. Standardized training and instructions will be provided to all subjects prior to administration of the WI-VAS assessments.

6.1.3 *Static Patient Global Assessment of Itch Severity*

The Static Patient Global Assessment of Itch Severity (sPGA) is designed to assess overall itch severity. Each subject is asked to rate the severity of his/her itchiness in the past 7 days on a 5-point scale as none, mild, moderate, severe, and very severe. Higher scores indicate greater itch severity. The sPGA scores will be captured on paper according to the schedule in [Appendix A](#).

6.1.4 *Patient Global Impression of Change in Itch Severity*

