8.8 Efficacy Analyses

All efficacy endpoints will be summarized within the FAP using descriptive statistics by time point and treatment.

8.8.1 *WI-NRS*

Subject record their WI-NRS measurements daily in an electronic diary. These daily measures are combined into weekly measures (Baseline, Weeks 2, 4, 6, 8, 10, Follow-up) by averaging the daily measurements. Change from baseline is the difference between baseline and the post baseline weeks. Missing data will be imputed as outlined in [Section 8.2](#). From this change from baseline the binary responder status (responder / non-responder) is created. A subject is a 4-point responder if their change from baseline is ≤ -4 (i.e. a decrease of at least 4). A 3-point responder is similarly defined. Subjects who withdraw from the study due to a lack of efficacy or require rescue therapy for treatment of worsening pruritus within four weeks prior to the timepoint will be defined as non-responders regardless of their change from baseline.

The daily WI-NRS endpoint (change from baseline in daily WI-NRS scores through Week 2) is the change between the baseline WI-NRS (same baseline as the weekly measures) and the daily measures over the first two weeks.

8.8.2 *Primary Efficacy*

The WI-NRS 4-point responder rate at Week 10 (primary endpoint) will be summarized by treatment group. The difference in responder rates between treatment arms will be tested using a CMH test controlling for the ‘as randomized’ stratification factors. Conceptually the hypotheses being tested are:

$$H_0: P_{Placebo} \geq P_{serlopitant} \quad H_a: P_{Placebo} < P_{serlopitant}$$

where $P_{Placebo}$ is the percent of placebo responders and $P_{serlopitant}$ is the similar percent for serlopitant.

Sensitivity analyses using other missing data rules will be performed.

8.8.3 *Secondary Efficacy and Exploratory*

Secondary endpoints will be summarized with descriptive statistics by time point and treatment. These summary measures will include baseline, result at the time point and change from baseline as is appropriate for the endpoint. Missing data imputation will be limited to the WI-NRS and WI-VAS endpoints.

The differences between treatment groups for the WI-NRS 4-point at Weeks 2, 4, 6, and 8, and 3-point responder rates at Weeks 2, 4, 6, 8, and 10 will be tested using the CMH test identical to the one used for the primary endpoint.

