2.3.7.2 Other Safety Endpoints

- Vital signs:
 - Systolic Blood Pressure, Diastolic Blood Pressure, Heart Rate, Respiration Rate, Height, Weight, Temperature and presence of a clinically significant abnormal values.
- 12-Lead Electrocardiogram:
 - RR, PR, QRS, QT, HR, QTcB, QTcF, and the ECG interpretation. A central read cardiologist assessment of normal vs abnormal will be available as well as an investigator assessment of clinically significant vs not clinically significant.
- Physical examination abnormalities identified as preexisting before treatment will be recorded as medical history. Abnormalities identified after treatment will be recorded as adverse events.

- Laboratory samples will include:
 - Hematology, Chemistry, Immunochemistry and Urine Pregnancy.

2.3.8 *Pharmacokinetic Measurements*

There will be one PK sample at the Week 10 visit. The plasma concentrations of serlopitant and metabolites M1/M1a, M2/M2a and M3 will be determined.

2.4 **Study Day and Visit Windows**

Summary tables will report data based upon the protocol scheduled time points (Baseline, Weeks 2, 4, 6, 10 and Follow-up). Assessment will be assigned to these time points based upon the study day they are performed on. The derivation of study day depends upon whether the event occurred prior to or after treatment. This results in the first day of treatment being on day 1 and the day prior to the first day of treatment being day -1. For events that occur prior to the first day of treatment the following definition is used,

$$\text{Study day} = \text{date of assessment} - \text{date of first treatment}.$$

For events that occur on or after the first day of treatment, a plus one is added,

$$\text{Study day} = \text{date of assessment} - \text{date of first treatment} + 1.$$

The analysis windows used to report non-daily endpoints are outlined in [Table 3](#). If more than one assessment is available within the range, the assessment closest to the target day is reported for the analyses window. If two observations exist with the same distance to the target day, the first observation is used.

Table 3 Analysis Windows

Visit	Range	Target Day
Screening	< Day - 7	First
Baseline	Day -7 to Day 1	Day 1
Week 2	Day 2 to Day 21	Day 15
Week 4	Day 22 to Day 35	Day 29
Week 6	Day 36 to Day 57	Day 43
Week 10	> Day 57	Day 71

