In addition to the analysis windows, data will be summarized at Follow-Up. The Follow-Up assessment will be the last assessment available that is at least seven days after the end of treatment. Should no post treatment assessments be available, the subject will not have a follow-up assessment. The baseline of an endpoint (see [Section 3.2](#)) may not always occur at the baseline visit.

The eDiary WI-NRS assessments will be summarized at Baseline, Week 2, 4, 6, 10, and Follow-up. The seven days leading up to the time point (see [Table 4](#) range), will be used to create the summary measures unless the subject does not have at least seven results. In this case, as many observations available within the complete data range will be used and additional data from the extended range (see [Table 4](#)) will be used until seven data points are achieved, or the end of the extended range is reached. An example of this algorithm can be found in [Section 3.4.1](#)

Table 4 Daily Windows

Visit	Range (complete data)	Extended Range
Baseline ^a	Day -7 to -1 or Day -6 to -1, Day 1	Day -11 to -8 or Day -10 to -7
Week 2	Day 8 to Day 14	Day 15 to Day 18
Week 4	Day 22 to Day 28	Day 29 to Day 32
Week 6	Day 36 to Day 42	Day 43 to Day 46
Week 8	Day 47 to Day 53	Day 54 to Day 57
Week 10	Day 64 to Day 70	Day 60 to Day 63

^a If the diary was completed prior to dosing on Day 1 then the baseline range includes the day of dosing (Day 1) otherwise the baseline range does not include Day 1.

An additional ‘Follow-Up’ timepoint will also be created. This timepoint includes the last 7 post treatment observations that are at least 7 days after the end of treatment.

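### A Day 1 diary score completed before dosing counts in the WI-NRS baseline and is also reported as Day 1 change from that baseline, which dilutes the Day 1 point of the daily series

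*SAP*

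**What the plan says.** **Baseline.** SAP Table 4 (section 2.4) gives two baseline windows for the diary score, "Day -7 to -1 or Day -6 to -1, Day 1". Its footnote a chooses between them by the order of diary and dose: "If the diary was completed prior to dosing on Day 1 then the baseline range includes the day of dosing (Day 1"). Otherwise Day 1 stays out. SAP 3.2 refers to Table 4 for the baseline of diary measures.

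**Daily series.** SAP 3.4.2 states: "The WI-NRS scores for days 1 to 14 will be plotted by averaging the available data across subjects within treatment group and study day". The accompanying table adds change from baseline, "where baseline is defined in the identical manner used for the weekly measures". The only selection rule given is data availability: "Daily WI-NRS results will be summarized in a table based upon availability of the data regardless of any intercurrent events".

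**Meaning of Day 1.** It is the calendar day of first dosing. SAP 2.4 says of its study-day rule: "This results in the first day of treatment being on day 1".

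**Endpoint and test.** Protocol 8.8.1 defines the daily endpoint as "the change between the baseline WI-NRS (same baseline as the weekly measures) and the daily measures over the first two weeks". Protocol 8.8.3 includes Days 1–14 in the ANOVA testing. SAP 2.3 lists the daily endpoint among the key secondary endpoints, and SAP 2.5 makes the p-values for those endpoints descriptive, without multiplicity adjustment.

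**Timing of the score.** Protocol 6.1.1 says of the scale: "It uses a 24-hour recall period". Each subject completes the diary at a roughly fixed time of day, within 3 hours either way. Nothing ties that time to the on-site first dose.

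**The concern.** The same diary entry serves as part of the reference and as the outcome compared with it. Putting a pre-dose Day 1 score into baseline is sound in itself. The trouble is that the score is then carried into the Day 1 row as well.

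The Day 1 row therefore pools two quantities. For subjects who filled in the diary after dosing, it is a first on-treatment score against an earlier average. For those who filled it in before dosing, it is a pre-dose score against an average that contains it. The mix depends on each subject's usual diary hour and on the time of the baseline visit.

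What is at stake is the first point of a curve that would be read for speed of onset, together with any test made at that point.

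**Working it through.** The plan gives no figure on this point, so there is none to reproduce. The stated power of at least 90% concerns the primary comparison, rests on responder rates that are blacked out, and is not an input here.

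**Step 1: trace the Day 1 score.**

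| Diary on Day 1 | Baseline window (Table 4) | Day 1 in baseline? | Day 1 in the daily series (SAP 3.4.2)? |
|---|---|---|---|
| Before dosing | Days −6 to −1 and Day 1 | Yes | Yes |
| After dosing | Days −7 to −1 | No | Yes |

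The first line is the overlap. No visible text drops the score from the Day 1 row, splits that row by dosing order, or starts the series at Day 2.

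**Step 2: the change for a pre-dose completer.** Let x1 be the Day 1 score and m6 the mean of Days −6 to −1, with all seven scores present.

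- Baseline = (6·m6 + x1)/7
- Day 1 change = x1 − (6·m6 + x1)/7 = (6/7)(x1 − m6)

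Both terms are pre-dose, so the change contains no drug effect. Its expected difference between randomized arms is zero, with or without the factor 6/7.

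**Step 3: the two kinds of change differ in spread.** Assume independent daily scores with within-subject variance 1 (an assumption, for illustration only).

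- Pre-dose completer: (6/7)² × (1 + 1/6) = 6/7 = 0.857
- Post-dose completer: 1 + 1/7 = 8/7 = 1.143

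A simulation of 400,000 subjects gave 0.857 and 1.143.

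**Step 4: dilution of the Day 1 treatment difference.** Let f be the share of subjects who complete the Day 1 diary before dosing, taken as equal in the two arms. Let D be the treatment difference among post-dose completers. The documents do not give f, so a range is shown.

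Day 1 difference = f × 0 + (1 − f) × D = (1 − f)·D

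| f | Share of D that remains | Subjects in the Day 1 row if pre-dose scores are left out, 200 × (1 − f) |
|---|---|---|
| 0.10 | 90% | 180 |
| 0.25 | 75% | 150 |
| 0.50 | 50% | 100 |
| 0.75 | 25% | 50 |
| 1.00 | 0% | 0 |

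**Step 5: reach.** Days 1–14 are 14 daily points, and one is affected. The first post-baseline weekly window in Table 4 opens at Day 8 and the Week 10 window covers Days 64–70 (extended range from Day 60). No post-baseline weekly average uses a Day 1 score.

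**The case against.** Several points against a stronger version are right.

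- **Labelling.** A reader might infer that the plan mislabels Day 1 as post-treatment. It does not. SAP 3.4.2 reports by study day, and footnote a itself classes a pre-dose Day 1 diary as baseline. The fault is double use of a score.
- **Drug exposure.** A reader might infer that any Day 1 comparison is made before the drug could act, or that every Day 1 recall window is mostly pre-dose. That holds only for pre-dose completers. Day 1 carries a three-tablet loading dose, and Protocol 1.3.2 puts peak plasma concentration at about 2 to 4 hours. A post-dose score may reflect some drug effect. How much of its recall follows dosing depends on clock times that the documents do not give.
- **The factor 6/7.** It is not a loss of treatment effect. It rescales noise and pre-dose drift alike in both arms. The dilution comes from f.
- **Direction.** The rule is the same in both arms, so it pulls the difference toward zero and does not create a false benefit.
- **Testing.** The visible SAP 2.5.2 wording names only the weekly time points for the WI-NRS ANOVA. Redacted text follows directly, so it cannot be inferred that the SAP dropped or kept the daily test. The planned test is taken from Protocol 8.8.3.
- **Materiality.** Onset would be read from the whole 14-day curve, and a near-zero first point is ordinary in such a display.

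These points limit the size and wording of the concern. They do not remove the overlap, which follows directly from Table 4 and SAP 3.4.2. The plan's other conventions do separate the two periods. Table 3 keeps Day 1 in baseline and starts Week 2 at Day 2. SAP 2.3.7.1 also separates adverse events on the first dosing day by whether they came after the dose.

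**Conclusion.** The point holds as a minor defect in one secondary analysis. Followed as written, the plan uses a pre-dose Day 1 score both in baseline and as Day 1 change, and the expected Day 1 treatment difference shrinks to (1 − f) of its value among post-dose completers.

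This rests on three assumptions: f is similar in the two arms, the expected pre-dose difference is zero under randomization, and (for the factor 6/7 only) seven baseline scores are present. The size cannot be narrowed further because f is not in the documents.

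The finding gives no reason to doubt the weekly results, the primary endpoint or the baseline definition.

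**What to change.** Add one sentence to SAP 3.4.2: a Day 1 score counted in the baseline average is not reported or tested as Day 1 change from baseline. Footnote a already requires the order of diary and dose to be known, so this is a filter in the code and needs no new data. Align Protocol 8.8.1 and 8.8.3, or record the clarification in the SAP.

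The alternative is to start the tested change series at Day 2, as Table 3 does for non-daily measures, and to show Day 1 only as an untested reference point. This is simpler but broader than the defect needs, since it also sets aside valid post-dose scores.

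The cost of the first option is a smaller Day 1 row, about 200 × (1 − f) subjects, which no longer holds the same subjects as later days; the table should show n by day. The cost of the second is one fewer descriptive comparison. Because of the 24-hour recall, the first option cleans the Day 1 row only in part: a retained post-dose score can still cover some hours before the dose.
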